3.3. Justification for Dose

Zilebesiran will be administered as a single dose of 300 or 600 mg SC in this study. These doses of zilebesiran have been selected for further evaluation in a planned Phase 2 study that will inform the doses selected for the Phase 3 program.

These doses were selected based on data from Study 001 and Study 002 that showed robust and durable reduction in serum AGT at these dose levels. Single and multiple doses of zilebesiran up to 800 mg in Study 001 and up to 600 mg in Study 002 were found to have acceptable safety profiles and lead to clinically meaningful reductions in 24-hour mean SBP by ABPM.

- In Study 001 Part A, single ascending doses of zilebesiran from 10 to 800 mg showed dose-dependent reductions in serum AGT and 24-hour mean SBP assessed by ABPM. Zilebesiran also demonstrated an acceptable safety profile at all dose levels. Based on Study 001 results, zilebesiran dose regimens of 150 mg q6M, 300 mg q6M, 600 mg q6M, and 300 mg q3M zilebesiran were selected to be evaluated in Study 002.
- In Study 002, a single dose of 300 or 600 mg zilebesiran (q6M regimens) showed clinically and statistically significant reductions in 24-hour mean SBP by ABPM compared to placebo at Month 3 (LS mean reductions of 16.7 mmHg for 300 mg and 15.7 mmHg for 600 mg) that were sustained through Month 6 (LS mean reductions of 14.5 mmHg for 300 mg and 14.2 mmHg for 600 mg). A dose-dependent reduction from baseline in serum AGT over time was observed across all the zilebesiran dose levels.
- For the proposed dose levels in this study, median reductions in serum AGT were 98.1% and 98.8% at Month 3 and 96.1% and 97.8% at Month 6 for the zilebesiran 300 and 600 mg doses, respectively. A log-linear relationship between reductions in serum AGT and change from baseline in 24-hour mean SBP by ABPM was observed in Study 002 leveraging data from all doses. Both regimens had acceptable safety profiles.

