6.5.6.2. Eliciting and Recording Adverse Events

Eliciting Adverse Events

The patient should be asked about medically relevant changes in the patient’s health since the last visit. The patient should also be asked if the patient has been hospitalized, had any accidents, used any new medications, or changed concomitant medication routines (both prescription and over-the-counter). In addition to patient observations, AEs will be documented from any clinically relevant laboratory findings, physical examination findings, ECG changes, or other findings that are relevant to patient safety.

Recording Adverse Events

The Investigator is responsible for recording non-serious AEs that are observed or reported by the patient after administration of the first dose of study drug regardless of their relationship to study drug through the patient’s EOS. Non-serious AEs will be followed until the patient’s EOS. Events occurring after signing of the ICF and before study drug administration will be captured

as medical history (see Section 6.1), while AEs that occur after study drug administration and baseline events that worsen after study drug administration must be recorded as AEs.

The Investigator is responsible for recording SAEs that are observed or reported by the patient after the time when the informed consent is signed regardless of their relationship to study drug through the patient's EOS. Refer to Section 6.5.6.4 for additional information regarding SAEs with a suspected causal relationship to study drug that occurs after a patient stops participation in the study or after the EOS. SAEs will be followed until satisfactory resolution, until baseline level is reached, or until the SAE is considered by the Investigator to be chronic or the patient is stable, as appropriate.

All AEs must be recorded in the source records for the clinical study center and in the eCRF for the patient, whether or not they are considered to be drug related. Each AE must be described in detail: onset time and date, description of event, severity, relationship to study drug, action taken, and outcome (including time and date of resolution, if applicable).

For SAEs, record the event(s) in the eCRF and, as applicable, the SAE form.

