2.1 Synopsis Study Design

This is a single dose, randomized, double-blind, placebo-controlled, parallel-group, Phase 1/2 study to evaluate the safety, tolerability, efficacy, PD, and PK of zilebesiran administered SC in Japanese patients with mild to moderate hypertension.

Before randomization, patients will discontinue prior antihypertensive medication(s) (if taking) for a Washout period of a minimum of 3 weeks. Patients who meet all inclusion criteria and none of the exclusion criteria will be randomized 1:1:1, to receive a single dose of 300 or 600 mg zilebesiran or placebo.

The planned enrollment for this study is 36 patients, each treatment arm will include 12 patients.

Study Design Schema

Abbreviations: aHTN=antihypertensive medications; BL=baseline; DB=double-blind; M=month; PD=pharmacodynamics; PO=per os (oral); R=randomization; SC=subcutaneous; SD=single dose; WO=washout. Note: Patients who were previously taking antihypertensives at screening must undergo a washout of these medications for a minimum of 3 weeks during the Screening period.

Below are the treatment groups and their definitions.

Name	Definitions
Placebo	Administered placebo on Day 1 of the 6-month DB Treatment Period.
Zilebesiran 300 mg	Administered 300 mg Zilebesiran SC on Day 1 of the 6-month DB Treatment Period.
Zilebesiran 600 mg	Administered 600 mg Zilebesiran SC on Day 1 of the 6-month DB Treatment Period.

Definition of study periods

Name	Definitions
Screening period	Before the administration of study drug
Double-Blind (DB) Period	From the administration of study drug until the end Month 6 visit (6-month period)
Safety/PD Follow-up	The 6-month period following the Month 6 visit.

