2.5 Safety Assessment

2.5.1 Adverse Events / Treatment-emergent Adverse Events / Serious Adverse Events / Adverse Events of Clinical Interest / Adverse Events Severity / Relationship of the Adverse Event to Study Drug

Item name	Definitions
Adverse Event	An AE is any untoward medical occurrence in a patient or clinical investigational subject administered a medicinal product and which does not necessarily have a causal relationship with this treatment.
Treatment-emergent Adverse Event	TEAE is defined as any AE occurring or worsening on or after the first dose of study drug upto 169 days after the study drug administration. Treatment related AEs that occur more than 169 days after the study drug administration (6-month DB period) are also counted as TEAE.
Serious Adverse Events	
A Serious Adverse Event is any untoward medical occurrence at any dose:
 
 • Results in death. • Is life-threatening (an event which places the patient at immediate risk of death from the event as it occurred. It does not include an event that had it occurred in a more severe form might have caused death). • Requires inpatient hospitalization or prolongation of existing hospitalization. • Results in persistent or significant disability or incapacity. • Is a congenital anomaly or birth defect. • Is an important medical event that may not be immediately life-threatening or result in death or hospitalization but may jeopardize the patient and may require intervention to prevent one of the other outcomes listed in the definition above (eg, events include allergic bronchospasm requiring intensive treatment in an emergency room or at home, blood dyscrasias, convulsions, or the development of drug dependency or abuse).

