3.5 Handling of time course data

3.5.1 Calculation of Number of Days

Number of Days is calculated by the following formula:

- If after first study drug administration date, Number of Days (n) = date of interest – first study drug administration date + 1
- If prior to first study drug administration date, Number of Days (n) = date of interest – first study drug administration date

Number of Days are negative when the day of interest is prior to first study drug administration date, positive when day of interest is after first study drug administration date. Number of Days never takes 0.

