3.5.2 Time Windows

For tables and figures, the visit will be defined as the following:

- For actual visits on EDC except unscheduled visit, end of treatment visit, early termination visit and end of study visit, the visit will be used as it is for analysis.
- For actual visits on EDC of unscheduled visits, the data from this visit will be used to calculate baseline, worst post baseline, and maximum post baseline only. Post baseline unscheduled visits will not be considered for by-visit analysis.
- For actual visits on EDC of end of treatment visit, early termination visit and end of study visit, the analysis visit will be as the following table. The day of administration of the investigational drug is defined as “Day 1”

Analysis visit	Reference date	Time window
Day 8	Day 8	Day 5 ~ Day 11
Day 15	Day 15	Day 12 ~ Day 18
Month 1	Day 29	Day 24 ~ Day 34
Month 2	Day 57	Day 52 ~ Day 62
Month 3	Day 85	Day 78 ~ Day 92
Month 4	Day 113	Day 106 ~ Day 120
Month 5	Day 141	Day 134 ~ Day 148
Month 6	Day 169	Day 162 ~ Day 176
Month 9	Day 253	Day 239 ~ Day 267
Month 12	Day 337	Day 323 ~ Day 351

For all listings, the visit will be displayed as the visit on EDC.

4. Statistical Analysis

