Definitions	:	
 • The denominator of proportions is the target population by groups.

12.4.3 Summary of Post-Baseline Potentially Clinically Significant Abnormalities for Clinical Laboratory Data during 6-Month DB Period

Target population	:	Safety Analysis Set
Analysis Items	:	Hematology, Serum Chemistry
Group	:	Placebo, Zilebesiran 300 mg, Zilebesiran 600 mg, Total zilebesiran, Overall Total
Time of analysis	:	Refer to section 2.8.1
Content of analysis	:	
 • Calculate the number of patients and the percentages by groups, analysis items and categories • Category for Hematology is as follows Hemoglobin (g/L): <100 Lymphocytes ($\times 10^9/L$): <0.8, <0.5, >12 Neutrophils ($\times 10^9/L$): <1.5, <1.0, ≥ 12 Platelet Count ($\times 10^9/L$): <75, <50, ≥ 600 WBC Count ($\times 10^9/L$): <3.0, ≥ 16 • Category for Serum Chemistry is as follows: Albumin (g/L): <30 Calcium (mmol/L): <2.0, >2.9 Creatinine (umol/L): >2xBaseline, >3xBaseline or >4 mg/dL eGFR(mL/min/1.73m²): $\geq 30\%$ Decrease from Baseline Plasma Glucose (mmol/L): <3.0, ≥ 13.9 Serum Glucose (mmol/L): <3.0, ≥ 13.9 Phosphate (mmol/L): <0.6 Potassium (mmol/L): <3.0, >5.5, >6.0 Sodium (mmol/L): <130, >155 • Calculate for Serum Chemistry with Confirmed by repeat measure is as follows: Creatinine (umol/L): >2xBaseline, Confirmed by repeat measure eGFR(mL/min/1.73m²): $\geq 30\%$ Decrease from Baseline, Confirmed by repeat measure Potassium (mmol/L): >5.5, Confirmed by repeat measure
Definitions	:	
 • The denominator of proportions is the target population by groups. • Repeat measure: the abnormal criteria was present for consecutive (non-missing) collections.

12.4.4 Shifts from Baseline to Worst Post-Baseline in eGFR (mL/min/1.73m²) during 6-month DB Period

Target population	:	Safety Analysis Set
Analysis Items	:	eGFR (mL/min/1.73m ²)
Content of analysis	:	
 • Create shift table for baseline to Worst post-baseline data by category. • Category is as follows: >=90 (mL/min/1.73m²), 60 to <90 (mL/min/1.73m²), 45 to <60 (mL/min/1.73m²), 30 to <45 (mL/min/1.73m²), 15 to <30 (mL/min/1.73m²), <15 (mL/min/1.73m²), Missing, Total
Definition	:	• The denominator of proportions is the target population by groups.

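### The treatment-emergent AE window can close up to 6 days before the double-blind period it is meant to cover, and no by-arm table counts all non-fatal AEs, whatever their cause, in Months 6–12

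*SAP*

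**What the plan says.** The primary endpoint is the frequency of patients with treatment-emergent AEs (Protocol 7.2.8). The Protocol gives that term no time window; the SAP supplies one.

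- **Window.** SAP 2.5.1 takes in "any AE occurring or worsening on or after the first dose of study drug upto 169 days after the study drug administration". SAP 3.3.1 repeats the limit as first administration + 169 days.
- **Exception.** "Treatment related AEs that occur more than 169 days after the study drug administration (6-month DB period) are also counted as TEAE". No end date is attached. SAP 3.3.1 treats missing relatedness as related.
- **Double-blind period.** SAP 2.1 defines it as "From the administration of study drug until the end Month 6 visit (6-month period"), which is a visit and not a fixed day. SAP 3.3.1 says that the AE summary tables cover the whole of this period.
- **Visit window.** SAP 3.5.2 gives "Day 162 ~ Day 176" for Month 6.
- **Collection.** Protocol 6.5.6.2 has non-serious AEs recorded when "observed or reported by the patient after administration of the first dose of study drug regardless of their relationship to study drug", through the patient's end of study. SAEs are also recorded to end of study.
- **Analyses.** SAP 2.4 plans a primary analysis once all patients have reached Month 6 or withdrawn, and a final analysis once all have completed the study or withdrawn.
- **Laboratory tables.** The titles of 12.4.2, 12.4.3 and 12.4.4 each limit them to the double-blind period. For example, 12.4.3 is headed "Summary of Post-Baseline Potentially Clinically Significant Abnormalities for Clinical Laboratory Data during 6-Month DB Period".

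**The concern.** There are two separate issues.

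First, the SAP treats 169 days and the double-blind period as the same thing, but its own definitions differ. A programmer cannot apply both the fixed limit and the statement that the tables cover the whole double-blind period. The rule affected decides who counts as having the primary endpoint.

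Second, after Day 170 entry into the AE tables depends on the Investigator's causality judgement. The final analysis then shows late related AEs by arm, but not all late AEs by arm. A concurrent placebo group is most useful where causality in a single patient is hard to judge, and Months 6–12 are such a period. Protocol 3.2 leaves the choice of escape antihypertensive to the Investigator after Month 6 (conventional RAS inhibitors remain prohibited). The Protocol 5.8.2 restriction on agents known to raise potassium ends at the end-of-treatment visit. For Study 002, Protocol 3.3 reports that "median reductions in serum AGT were 98.1% and 98.8% at Month 3 and 96.1% and 97.8% at Month 6", so the pharmacological effect was still strong when the window closes. A late potassium, blood-pressure or renal event could reasonably be put down to an added drug and so leave the by-arm AE count.

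**Working it through.** **1. The cut-off as a study day.** SAP 3.5.1 sets "Number of Days (n) = date of interest – first study drug administration date + 1". For a date 169 days after dosing, n = 169 + 1 = 170, so the window closes on Day 170.

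**2. The Month 6 window.** The Protocol schedule gives Day 169 ± 7: 169 − 7 = 162 and 169 + 7 = 176. This reproduces the SAP window.

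**3. The mismatch.** 176 − 170 = 6 days (Days 171–176), which is 6 of the 15 days in the window. In the other direction, a patient seen on Day 162 has a treatment-emergent window that runs 170 − 162 = 8 days past the visit.

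**4. Size of the 6-day gap.** The documents give no overall AE rate for this trial. Assume a constant hazard, with a proportion p of patients having an AE by Day 170. The proportion by Day t is then 1 − (1 − p)^(t/170). For an arm of 12, the patients added by extending to Day 176 are 12 × [(1 − p) − (1 − p)^(176/170)]:
- p = 0.2: 12 × (0.2063 − 0.2) ≈ 0.08
- p = 0.6: 12 × (0.6127 − 0.6) ≈ 0.15

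Over p = 0.2 to 0.7 the range is about 0.08 to 0.15 patients per arm, even if every visit were on Day 176 and every such AE were unrelated.

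**5. Time after the cut-off.** To nominal Month 12: 337 − 170 = 167 days, and 167/337 = 49.6%. Across the Month 12 window (Days 323–351) this is 153 to 181 days, or 47% to 52%.

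Under the same assumption, a patient count that ran to Day 337 would add 1.9 patients per arm at p = 0.2 and up to 3.0 at p = 0.5. This is an upper bound, because late related AEs already count.

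**6. What covers Months 6–12, output by output.**
- *AE tables 12.1.1–12.1.4 and 12.1.6:* treatment-emergent only, so late non-fatal unrelated AEs and SAEs are absent. Deaths in 12.1.1 are exempt. The injection-site table 12.1.5 is not labelled treatment-emergent.
- *AE listings (3.3.1, section 13):* all AEs from screening through follow-up.
- *12.4.1 by-visit chemistry and liver tests:* Months 9 and 12 included (2.8.1), by arm, with minimum and maximum (4.1.1).
- *12.4.6 mean plots of liver tests, eGFR and potassium:* follow-up included.
- *12.4.5 liver abnormalities, 12.4.7 eDISH plot, 12.2.3 vital-sign abnormalities:* no limit to the double-blind period.
- *12.4.2–12.4.4 shifts, potentially significant values and eGFR shifts, and 12.4.9 potassium plot:* double-blind period only.

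Two things are therefore missing for Months 6–12: a by-arm, all-causality AE count, and by-arm counts of patients crossing the potassium, creatinine and eGFR thresholds.

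**The case against.** The case for leaving the plan alone is substantial.

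- **A reader might infer that the primary endpoint is under-counted.** The documents do not support that. The Protocol sets no treatment-emergent window, Protocol section 7 speaks of a primary analysis of the 6-month double-blind period, and the SAP limit equals its exposure end in 2.5.2. Collecting AEs to end of study does not make them all treatment-emergent. There would be an under-count only if the endpoint were meant to span 12 months, and nothing says so.
- **A reader might infer that late safety events are hidden.** They are not: step 6 of the working lists the outputs that show them, and late related AEs stay in the by-arm tables.
- **A reader might carry forward the 5.6% of Study 002 zilebesiran patients with potassium above 5.5 mmol/L (0.056 × 24 = 1.3 patients).** That is a laboratory rate, not an AE rate, and it pools regimens that include two doses. Here there are 8 scheduled post-dose chemistry visits to Month 6 and only 2 afterwards. Protocol 1.2 also says that most Study 002 hyperkalaemia events were judged related, and such events would still count.
- **Bias between arms is not shown.** Investigators stay blinded to the end of the study (Protocol 3.5), and the analyses are descriptive.
- **Activity after Month 6 is an inference.** AGT suppression is documented only up to Month 6.

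All of this stands. It limits the point to an inconsistency in definition and a missing comparison. It does not reconcile SAP 2.1 with 2.5.1, and it does not supply a by-arm, all-causality count for the second half of follow-up.

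**Conclusion.** The concern holds in limited form. The all-causality window closes on Day 170 and the double-blind period can run to Day 176. The two rules need reconciling because they govern the primary endpoint, but the effect is small: about 0.08–0.15 patients per arm under the assumed constant hazard and 20%–70% AE incidence.

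The more useful part is Months 6–12. For about 167 of 337 nominal days, non-fatal AEs and SAEs judged unrelated enter no by-arm treatment-emergent table, and laboratory threshold counts stop at Month 6. This loses a comparison that the collected data could provide. It is not evidence of a wrong primary result or of concealed events. The change is a cheap improvement, and the 6-month primary analysis does not depend on it.

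**What to change.** - In SAP 2.5.1 and 3.3.1, end the all-causality window at each patient's actual Month 6 visit date, or at dose + 169 days if there is no Month 6 visit. Keep the 6-month treatment-emergent analysis as primary.
- At the final analysis, add by-arm tables of AEs and SAEs regardless of relatedness, from Month 6 to end of study or for the full study.
- Add full-study versions of 12.4.2–12.4.4 that include Months 9 and 12.
- Specify these before the unblinded primary analysis, so that they are not added after results are known.

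The cost is SAP wording and a few repeat tables; all the data are already collected. The follow-up tables will contain more background events and effects of escape medication, and should be read with that in mind. A visit-based cut will differ by a few days from the exposure definition in 2.5.2, which a footnote can state. Patients seen before Day 170 will have some events move from the 6-month table to the follow-up table.

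Extending the primary treatment-emergent definition itself to end of study is not needed: it would change the endpoint's time frame and break its alignment with exposure.

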7.2.8. Safety Analyses

The primary endpoint is the frequency of patients with treatment-emergent AEs (hereafter referred to simply as AEs). Safety assessments also include vital signs, ECGs, clinical laboratory assessments, and physical exams. Extent of exposure will be summarized by dose level and overall.

Prior and concomitant medications will be coded using the World Health Organization Drug Dictionary. Results will be tabulated by Anatomical Therapeutic Chemical Classification System and Preferred Term (PT).

Adverse events will be coded according to the Medical Dictionary for Regulatory Activities and summarized by System Organ Class (SOC) and PT by dose level and overall. AEs, SAEs, study-drug related AEs, AEs leading to withdrawal from study, and AEs leading to death will be summarized by SOC and PT for each treatment arm and overall. By-patient listings will be provided for deaths, SAEs, and AEs leading to withdrawal from study.

Descriptive statistics will be provided for clinical laboratory parameters, ECG, and vital signs summarizing the observed values and changes from baseline over time. Laboratory shift tables from baseline grade (or category) to worst postbaseline grade (or category) will be presented for laboratory parameters that are graded or categorized.

Other safety summaries will be presented as appropriate. Further details will be specified in the SAP.

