2.4 Analysis time point

The primary analysis will be performed when all patients complete the Month 6 visit or withdraw from the study prior to the Month 6 visit.

The final analysis will be performed when all patients complete the study or withdraw from the study.

A patient is considered to have completed the study if:

- The patient has completed the Month 12 visit (EOS).

- The Investigator, in conjunction with the Sponsor's Medical Monitor, makes a recommendation on a case-by-case basis to discontinue follow-up.

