3.3 Handling of Safety Data

3.3.1 Handling of Adverse Events

Adverse events will be coded according to the Medical Dictionary for Regulatory Activities and summarized by System Organ Class (SOC) and PT by dose level and overall. AEs, SAEs, study-drug related AEs, AEs leading to withdrawal from study, and AEs leading to death will be summarized by SOC and PT for each treatment arm and overall. Additionally Hepatic AEs, including AEs of LFT abnormalities, Hyperkalemia, Hypotension, Potential Hypotension and Acute renal failure will be summarized by SOC and PT for each treatment arm and overall. AEs, SAEs, and study-drug related AEs will be summarized by PT for each treatment arm and overall. By-patient listings will also be provided.

1) For summary tables

Treatment-emergent Adverse Event from throughout the double-blind treatment period will be included.

- First study drug administration date Onset date of Adverse Events \leq first study drug administration + 169 days.
- Treatment related AEs that occur after 169 days of first study drug administration are also counted as TEAE.

AEs with Missing or partial dates will be handled per section 3.1.1.

An AE with missing severity will be assumed to be severe.

An AE with missing study drug relatedness will be assumed to be related.

2) For listings

All Adverse Events from screening period through safety-follow up period will be included.

Missing study drug relatedness and missing severity will be presented as collected in the EDC.

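### The all-causality TEAE window closes at Day 170, up to six days before the double-blind period can end, and later non-fatal AEs judged unrelated reach listings but no by-arm AE table

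*SAP*

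**What the plan says.** SAP 2.5.1 defines a TEAE as "any AE occurring or worsening on or after the first dose of study drug upto 169 days after the study drug administration" and then adds: "Treatment related AEs that occur more than 169 days after the study drug administration (6-month DB period) are also counted as TEAE". SAP 3.3.1 repeats the rule for the summary tables, with onset no later than first administration plus 169 days, and adds: "Treatment related AEs that occur after 169 days of first study drug administration are also counted as TEAE". The same subsection introduces those tables as covering the whole double-blind treatment period.

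SAP 2.1 defines that period differently: "From the administration of study drug until the end Month 6 visit (6-month period"). It ends at a visit, not on a fixed day. SAP 3.5.2 gives the Month 6 window as "Day 162 ~ Day 176".

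Protocol 7.2.8 states: "The primary endpoint is the frequency of patients with treatment-emergent AEs". The protocol attaches no day limit or causality condition to that. Protocol 6.5.6.2 has investigators record non-serious AEs "observed or reported by the patient after administration of the first dose of study drug regardless of their relationship to study drug" through the patient's end of study. SAEs are recorded on the same basis from consent.

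On timing, SAP 2.4 says: "The primary analysis will be performed when all patients complete the Month 6 visit" or have withdrawn before it. A final analysis follows when all patients have finished the study.

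**The concern.** Two things do not fit together. First, the fixed cut and the visit-based period are both meant to describe the same six months, but the cut can fall before the visit. Many laboratory-detected AEs come to light at a visit, and after Month 5 the next scheduled chemistry and liver tests are at Month 6. A patient seen on Day 173 with a new potassium or eGFR abnormality judged unrelated would have it in the double-blind laboratory table (SAP 12.4.3) but not in the TEAE tables.

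Second, after the cut the endpoint changes meaning: events of any cause before it, only events the investigator calls related after it. The filter starts while the pharmacology is still active. Protocol 3.3 reports median serum AGT reductions of 96.1% (300 mg) and 97.8% (600 mg) at Month 6 in Study 002. The hepatic, hyperkalemia, hypotension and renal-failure tables in SAP 12.1.2 are all TEAE tables, so they inherit the filter.

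A smaller point follows from the same clause. It has no end date. At the primary analysis, patients enrolled early may already have contributed late related events that patients enrolled late cannot yet have had.

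**Working it through.** **Inputs.** TEAE cut: dose date + 169 days (SAP 2.5.1, 3.3.1). Day numbering: date minus first dose date, plus 1 (SAP 3.5.1). Month 6 window: Days 162-176, nominal Day 169. Month 12 window: Days 323-351, nominal Day 337 (SAP 3.5.2). Patients per arm: 12.

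**The cut as a study day.** 169 + 1 = Day 170, one day after the nominal Month 6 visit.

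**Overlap with the Month 6 window.** Permitted days: 176 − 162 + 1 = 15. Inside the cut: Days 162-170, 9 days. Outside: Days 171-176, 6 days, and 6/15 = 40%. This is a share of calendar days. It is a share of visits only if visits are spread evenly over the window, which the documents do not say.

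**Length of the related-only period.** (end of study − 170) / end of study:

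- nominal Day 337: 167/337 = 49.6%
- earliest, Day 323: 153/323 = 47.4%
- latest, Day 351: 181/351 = 51.6%

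**How many late AEs this removes.** If a share r of post-cut AEs is called related, 1 − r is left out of the tables. The documents give no r for this trial, so the values below are assumptions. The last column also assumes a constant AE rate through Day 337, and is (167/337) × (1 − r).

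| Assumed r | Post-cut AEs not tabulated | Share of all AEs to Day 337 |
|---|---|---|
| 0.10 | 90% | 45% |
| 0.25 | 75% | 37% |
| 0.50 | 50% | 25% |
| 0.75 | 25% | 12% |
| 0.90 | 10% | 5% |

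**Effect on the patient-level endpoint.** One patient is 1/12 = 8.3 percentage points of an arm. That is the most one missed patient can cost, and only if the missed event is that patient's sole AE. Anyone with a TEAE by Day 170 is already counted.

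**After the change.** With the window run to the Month 6 visit and never shorter than Day 170, 0 of the 15 permitted visit days fall outside it. The whole-study table covers 337 of 337 nominal days for any causality, against 170 of 337 (50.4%) now.

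**The case against.** The best defence is that the SAP made a choice and the information survives elsewhere. The protocol's primary analysis is of the 6-month double-blind period, it sets no TEAE window, and it leaves detail to the SAP. The cut agrees with SAP 2.5.2, which caps exposure at last dose + 169 days. The rule is identical in every arm, investigators are blinded to the end of study, AGT results are withheld from sites, and the analyses are descriptive.

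Much is also retained. Missing relatedness counts as related (SAP 3.3.1). All fatal SAEs are summarized whatever their treatment-emergent status (SAP 12.1.1). Chemistry and liver tests are summarized by arm and visit to Month 12 (SAP 2.8.1, 12.4.1), and the mean plots of liver tests, eGFR and potassium extend into follow-up (SAP 12.4.6). The disposition summary counts follow-up withdrawals for AEs by arm (SAP 5.2). Every AE through follow-up is listed, for a trial of 36 patients.

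All of that stands, and it rules out two stronger readings that a reader might infer. One is that Month 6 findings as such fall out of the primary endpoint. They do not: visits through Day 170 are fully inside the cut, and a later event is lost only if its onset is on Days 171-176 and it is judged unrelated. The other is that most harms in the second half of follow-up go uncounted. That needs r below 0.5, which no document supports. Earlier relatedness calls point both ways: Protocol 1.2 reports most hyperkalemia events in Study 002 as related, and the AEs associated with ALT/AST elevations in Study 001 as not related. It could also be suggested that investigators who see blood pressure would judge relatedness differently by arm; that is possible, but nothing in the documents shows it.

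The defence does not reconcile SAP 2.5.1 and 3.3.1 with SAP 2.1, and it does not supply an all-causality AE table for follow-up. Laboratory summaries do not replace one: they do not show symptomatic events or non-fatal SAEs.

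**Conclusion.** The concern holds in a limited form and should be fixed. The SAP's all-causality TEAE window stops at Day 170, while its own double-blind period can run to Day 176 and its AE tables claim to cover that period. The direct exposure is six of 15 permitted visit days, and within those only new events judged unrelated. Beyond that, for 167 of 337 nominal days (47.4% to 51.6% across the end-of-study window), non-fatal AEs and SAEs judged unrelated are listed but not tabulated by arm, although the protocol collects them.

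The day counts rest only on the SAP's day numbering and visit windows. The number of events lost cannot be derived from the documents. A 6-month primary period is a legitimate design choice and is not criticized here.

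**What to change.** In SAP 2.5.1 and 3.3.1, define the 6-month TEAE as any AE, whatever its causality, with onset or worsening from first dose through the later of Day 170 and the Month 6/EOT visit date, using Day 176 where there is no Month 6 visit. The later-of rule matters: a cut at the visit date alone would, for a Day 162 visit, lose events on Days 163-170 that are counted now.

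Report the 6-month count without the causality-filtered late events. Repeat tables 12.1.1 and 12.1.2 by arm, for all AEs and SAEs whatever the causality, for the follow-up period and for first dose through Month 12/EOS. Late related events then stay in the tables, beside the unrelated ones.

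The cost is SAP wording and one extra table set on data already collected. The new tables need a footnote that antihypertensives of the investigator's choice are allowed in follow-up.
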